10.2. Data collection overview

The documentation of study data will be reported by the attending physician via paper or electronic case report form (CRF).

Term	Baseline visit (V1)	Observational visit (V2)	Observational visit (V3)	Final Observational visit (V4)
Inclusion/exclusion criteria	X			
Signed Informed consent form	X			
Date of visit	X	X	X	X
Demographic information	X			
Medical history (incl. risk factors, prior diseases, prior HTN therapy etc)	X			
Body Mass Index (BMI)	X	X	X	X
Physical examination and vital signs*	X	X	X	X
HTN therapy (drugs, doses)	X	X	X	X

Laboratory tests and instrumental exams*	X	X	X	X
Concurrent medical conditions	X			
Concomitant medication		X	X	X
Adverse events		X	X	X

* All examinations (physical examination and vital signs, laboratory tests and instrumental exams) are done in accordance with clinical routine practice and physician's decision. Instrumental exams are measurement of blood pressure, heart rate, ECG, 24-hour ambulatory blood pressure monitoring. All examinations should be registered in the CRF only if they are done in routine practice.

10.3. Data collected on the Baseline visit

Baseline visit is a visit after physician makes a decision to prescribe Edarbi® for HTN treatment. It means that investigator inform patient about the study only after taking decision about strategy of HTN treatment.

Data to be collected:

- Date of visit (day, month, year)
- Date of Informed consent form signing (day, month, year)
- Compliance with Inclusion/exclusion criteria
- Demographic information: sex, date of birth, ethnicity, region of residence (city, town etc)
- Medical history:
 - History of HTN
 - Duration of HTN/first diagnosed
 - Presence of HTN target organ damage
 - Risk factors of cardiovascular disease (smoking, dyslipidaemia, glucose intolerance, obesity, abdominal obesity, family history of cardiovascular disease,)
 - Cardiovascular diseases history:
 - established cardiovascular diseases (coronary artery disease, chronic heart failure, arrhythmias, peripheral artery diseases, ischemic heart disease etc.)
 - history of cardiovascular events (myocardial infarction, stroke, etc.)
 - Alcohol use
- Diagnose of HTN: grade, stage, risk.
- Physical examination and vital signs: height (cm), weight (kg), waist circumference (cm), body mass index, systolic and diastolic blood pressure (position, time, values), heart rate, physical inactivity

- HTN treatment:
 - previous HNT-treatment (if applicable),
 - reason(s) for discontinuation of previous HNT-treatment (if applicable),
 - monotherapy/combination treatment,
 - Edarbi® dosage regimen,
 - other HTN co-medications: INN, trade name, dosage regimen (if applicable).
- Laboratory data (last available measurements, if done within routine practice):
 - total cholesterol,
 - triglycerides,
 - low-density lipoproteins,
 - high-density lipoproteins,
 - blood glucose,
 - serum creatinine,
 - urea,
 - glycated haemoglobin
- Concurrent medical conditions (diabetes mellitus, chronic kidney disease, chronic obstructive pulmonary disease, etc.)
- Concomitant medication: INN, trade name, dosage regimen (single and total daily dose), duration of treatment, indication for administration
- Adverse events: seriousness, severity, causality, start and stop dates, action, outcomes

10.4. Data collected on the Observational visits 2, 3 and 4

Data to be collected:

- Date of visit (day, month, year)
- Diagnose of HTN: grade, stage, risk.
- Physical examination and vital signs: height (cm), weight (kg), waist circumference (cm), body mass index, systolic and diastolic blood pressure (position, time, values), heart rate
- HTN treatment:
 - monotherapy/combination treatment,
 - Edarbi® dosage regimen,
 - other HTN co-medications: INN, trade name, dosage regimen.
- Laboratory data (last available measurements, if done within routine practice):
 - total cholesterol
 - triglycerides,

- low-density lipoproteins,
- high-density lipoproteins,
- blood glucose,
- serum creatinine,
- urea,
- glycated haemoglobin.
- Concomitant diseases
- Concomitant medication: INN, trade name, dosage regimen (single and total daily dose), duration of treatment, indication for administration
- Adverse events: seriousness, severity, causality, start and stop dates, action, outcomes

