10.6.6. Pregnancy

If any patient is found to be pregnant during the study she should be withdrawn. The pregnancy should be reported immediately, using an AE report form.

All pregnancies in patient on active study drug will be followed up to final outcome. The outcome, including any premature termination, must be reported to the Sponsor. An evaluation of child wellness after the birth must be reported to the Sponsor.

10.7. Laboratory, instrumental exams, physical examination and vital signs to be documented in the study

All examinations (physical examination and vital signs, laboratory tests and other exams) will be performed in accordance with common clinical routine practice, routine practice of a particular medical institution. All examinations are solely based on the physician's decision about strategy of diagnostics and treatment.

All examinations should be registered in the CRF only the protocol required lab tests will be recorded in the CRFs if they are done in routine practice. The documentation of laboratory and instrumental tests will strictly follow clinical practice. The reference ranges for each protocol required lab test performed according to routine practice will be collected as well.

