5. STATISTICAL / ANALYTICAL ISSUES

Visit windows

In accordance with the protocol, due to the non-interventional study design it's not possible to appoint exact times for the study visits, although it is expected that the period of observation will be approximately 6 months. The frequency of the visits will be assigned by each physician according to their routine practice. It is anticipated that the patients will visit their physician every 3 months and more often at the beginning until the patient achieves target blood pressure.

So, for the analysis and summary of clinical laboratory, efficacy, and safety data in case of this analysis/summary performed on "by visit" base. In the event of multiple values for an assessment within an analysis window, the value closest to the scheduled visit date will be used for analyses. If two values tie as closest to the time point (for example, one value is before and the other value is after the time point), then the later value will be selected as the analysis value.

Analysis Window	Start	End	Target Asses dupli	sment to be used if cates	
Baseline visi	t <1		NA		
Month 1 Month 3 Month 6	2 46 136	45 135 NA	30 90 Closes 180 equidi	st to target day, if stant use later result.	

The definition for the study days included in each study window is defined as below:

Treatment Day prior to first dose = Visit Date – Date of First Dose

Treatment Day on or after first dose = Visit Date – Date of First Dose + 1

Adjustments for Covariates

No specific adjustments for covariates will be made in all statistical analyses, unless specified otherwise per-analysis level.

Handling of Dropouts or Missing Data

Missing efficacy outcomes will be assumed to be missing at random (MAR) and thus will not be imputed in the primary analysis. However, if greater than 1% of all primary/secondary outcomes that should be available for analysis are missing, a sensitivity analysis will be undertaken in addition to the primary MAR analysis.

Confidential

This sensitivity analysis will include an evaluation of the results of models developed under the assumptions of:

1) last observation carried forward;

2) worst extreme case imputation and;

3) regression model imputation using all available information.

Outlier identification

During data Quality Control outlier identification will be performed using adjusted Z-score method (Iglewicz and Hoaglin, 1993).

$$M_i = \frac{0.6745(x_i - \tilde{x})}{MAD}$$

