- Changes in serum creatinine, eGFR (CKD-EPI), urea, total cholesterol, triglycerides, low density lipoproteins, high density lipoproteins (from baseline to Month 1- Month 3- Month 6) will be assessed and presented in summary tables using descriptive statistics for continuous variables. Additionally the changes of this variable will be analyzed with paired T-test in pairwise comparisons with baseline level of the variable.
- Changes of blood glucose level, glycated hemoglobin (HbA1c) from baseline to the visits 2, 3, and 4. For the analysis 95% Cis will be constructed. Additionally the changes of this variable will be analyzed with paired T-test in pairwise comparisons with baseline level of the variable.

9.0 Analysis of BMI and waist circumference change from baseline to visit 4. 95% CIs will be constructed. Additionally the changes of this variable will be analyzed with paired T-test in pairwise comparisons with baseline level of the variable.

10. Reasons for discontinuation of Edarbi[®] therapy will be described and presented in summary tables using absolute frequencies and percentages as well as 95% confidence intervals.

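### Follow-up laboratory results carry no required sample date and are windowed by visit date, so a pre-dose or already-used sample can be analysed as a Month 1, 3 or 6 value

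*Protocol*

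**What the plan says.** **Collection.** Protocol 10.3 (baseline) and 10.4 (visits 2 to 4) use the same rule: "Laboratory data (last available measurements, if done within routine practice"). Neither section limits the age of the sample, asks for a draw after first dose, or bars re-entering a result already recorded. The date listed in both sections is that of the visit, "Date of visit (day, month, year"). For laboratory tests, protocol 10.7 adds one further item: "The reference ranges for each protocol required lab test performed according to routine practice will be collected as well". No repeat test is required. The footnote to the schedule in 10.2 reads "All examinations should be registered in the CRF only if they are done in routine practice".

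**Windows.** SAP section 5 applies its visit windows "for the analysis and summary of clinical laboratory, efficacy, and safety data". Month 1 is day 2 to 45, Month 3 is day 46 to 135, and Month 6 is day 136 onward with no end day. Study day is defined by "Treatment Day on or after first dose = Visit Date – Date of First Dose + 1". If several values fall in a window, the one nearest the target day is kept. The age of the sample plays no part.

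**Analysis.** SAP 9.2 covers "Changes in serum creatinine, eGFR (CKD-EPI), urea, total cholesterol, triglycerides, low density lipoproteins, high density lipoproteins" from baseline to each follow-up month, with descriptive statistics and paired t-tests. For glucose and HbA1c it adds 95% confidence intervals to the paired t-tests. SAP 9.3.1 repeats these analyses in many subgroups, and SAP section 11 asks for p-values between subgroups.

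**The concern.** In routine care many patients will not have blood drawn between visits. For such a patient, the most recent result at visit 3 may be the one entered at visit 1. Read literally, the rule lets the site enter it again, and the SAP then treats it as a Month 3 measurement.

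Both documents say that missing data are not imputed in the main analysis (protocol 13.2.5.1; SAP section 5). A reused result is in effect a carried-forward value that is never flagged, because the field is filled.

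At stake is the description of renal, lipid and glycaemic change on treatment. An average change diluted by repeated baseline values, with an interval that looks precise, would understate whatever change occurred. If testing frequency differs between, say, diabetic and non-diabetic patients, the dilution differs too and can look like a subgroup effect.

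**Working it through.** **The plan's own figures.** The documents give no figure for laboratory changes. The only sizing is for SBP (protocol 13.4), and it reproduces:

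- SD of the difference = 17.79 × √(2 × (1 − 0.4375)) = 18.869.
- The smallest n giving a half-width of 1 mm Hg with conditional probability 0.90 is 1437 (computed probability 0.9027; plan 0.903).
- 1437 / 0.75 = 1916.

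No laboratory value enters this calculation.

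**How a stale value gets through.** Suppose a sample is drawn the day before first dose and entered again at a visit 89 days after first dose.

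- By visit date, the study day is 89 + 1 = 90, so the value is analysed as Month 3.
- By sample date, the pre-dose formula "Treatment Day prior to first dose = Visit Date – Date of First Dose", with the sample date in place of the visit date, gives −1, which belongs to baseline.

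The windows cannot remove the value, because they never see the sample date.

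**What reuse does to one patient's change.**

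- Baseline sample reused: the change is 0.
- Month 1 sample reused at Month 3 or 6: the Month 1 change is repeated.

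**Effect on the summary when the baseline sample is reused.** Let q be the share of N follow-up values that repeat the baseline sample. This is an assumption, since the documents give no figure. Let the remaining changes have mean μ and SD σ, and let d = μ/σ.

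- Mean of all changes = (1 − q)μ.
- Variance = (1 − q)(σ² + μ²) − (1 − q)²μ² = (1 − q)(σ² + qμ²).
- The comparator is the analysis of fresh samples only, which has mean μ, SD σ and (1 − q)N pairs.
- Ratio of CI widths = (1 − q)√(1 + qd²).
- Ratio of paired t-statistics = 1/√(1 + qd²).

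| q (assumed) | Mean × | CI width ratio, d = 0.2 | t ratio, d = 0.2 | CI width ratio, d = 0.5 | t ratio, d = 0.5 |
|---|---|---|---|---|---|
| 20% | 0.80 | 0.803 | 0.996 | 0.820 | 0.976 |
| 30% | 0.70 | 0.704 | 0.994 | 0.726 | 0.964 |
| 50% | 0.50 | 0.505 | 0.990 | 0.530 | 0.943 |

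For a small change (d = 0.2) the interval is about 20%, 30% or 50% too narrow, and it is centred on a mean that is too small by the same share. The t-statistic loses 1% or less. The values of d are also assumptions.

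**Subgroups.** If two subgroups have the same true change μ but reuse shares q₁ and q₂, their observed means differ by (q₂ − q₁)μ. With assumed shares of 20% and 50%, a spurious difference of 0.3μ appears.

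This model does not cover reuse of a Month 1 sample. The error there depends on how the Month 1 change compares with the later one.

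**The case against.** **The collection rule can be read more strictly.** Results are recorded only if testing is done in routine practice, and laboratory tests are scheduled by visit. A site could reasonably leave the field blank when nothing new was drawn. This stands in part: the protocol permits reuse but does not direct it, and practice may differ between sites. The qualifier sets no time limit, however, and does not override the rule to take the latest result on file.

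**A sample date may exist.** The CRF and Data Management Plan are not among the documents. Laboratory forms are source data, and the logic checks look for inconsistent dates. So one cannot conclude that no date is captured, only that none is listed. Even with such a date, the SAP assigns windows by visit date.

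**Scope.** Laboratory changes are not among the listed primary or secondary outcomes, and the exploratory outcomes are redacted. SAP 9.2 treats secondary and exploratory variables together. The SAP also says that it will be applied to the Kazakhstan data, so the windowing problem is shown for that analysis, whereas the collection rule is study-wide.

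**Stronger readings that do not hold.**

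- A reader might infer that a real shift would be missed by the test. Against the fresh-sample analysis, the t-statistic falls only to 0.99 at q = 50% and d = 0.2. Against N fresh samples it would fall to 0.70, but those samples do not exist and no analysis rule can supply them.
- A reader might infer that every reused sample forces a zero change. That is so only when the baseline sample is reused.
- A reader might infer that the blood pressure results are compromised. The rule is attached to laboratory data alone.

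**Conclusion.** The point holds for the laboratory-change analyses. As written, the two documents allow a sample drawn before first dose, or one already used, to be analysed as a Month 1, 3 or 6 value, and the visit windows cannot screen it out. When the baseline sample is reused at rate q, the mean change is multiplied by 1 − q. For small standardized changes, the interval is about q too narrow relative to fresh samples only.

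The harm is to the estimates, their intervals and the subgroup contrasts, and not mainly to the paired test. SAP 9.2 names intervals expressly for glucose and HbA1c; for the other analytes the same distortion affects the reported mean and SD.

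The size rests on q, which the documents do not give, and on a model in which reuse is unrelated to the size of the true change. The SBP primary outcome, DBP and the sample size are not touched. The change is worth making, but it does not threaten the study's main result.

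**What to change.** 1. Record the sample date for each laboratory result. For data already collected, query the date from source.
2. In SAP section 5, compute the study day of laboratory values from the sample date.
3. Accept a follow-up value only if it was sampled after first dose and has not been used at an earlier visit. Treat the rest as missing. A rule requiring the sample to follow the previous visit would be too strict: it could discard a valid post-dose sample drawn at that visit but reported later.
4. Report, by window, how many results were set aside under this rule, overall and by subgroup.
5. Where dates cannot be recovered, add a sensitivity analysis without follow-up values identical to baseline. It can serve only as a sensitivity analysis, because some identical values will be genuine.

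No additional test is required, so the non-interventional design is unaffected. The cost is date entry and fewer laboratory pairs. Eight analytes are listed at four visits, so there are at most 8 × 4 = 32 dates per patient, and fewer if tests share a sample. The entry falls on paper and electronic CRFs at about 90 sites. Some subgroup tables may become too sparse to report.

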10.5. Data collected on the End of observation

The end of observation in this study should be documented when:

- Voluntary withdrawal of informed consent in patient’s request or at the request of patient’s legally acceptable representative;
- Development of exclusion criteria or other safety reasons (not a AE or SAE) during the study;
- Adverse Events (AE)/ Serious Adverse Events (SAE) that requires early termination because patient is unwilling to continue because of the AE or SAE or continuation of patients’ visit to the clinic is impossible or any other occurrence which can be happened;
- Lost for observation within the framework of the study. The patient did not return to the clinic and attempts to contact the patient were unsuccessful;
- Patient’s death;
- Study termination. Sponsor decision or regulatory authorities’ requirement about cessation of the study;
- Pregnancy;
- Premature end of HTN treatment by Edarbi®,
- End of HTN treatment by Edarbi®,

In case if one of described above events become, investigator should fill in the last appropriate Observational visit Form and the “End of observation” Form.

The following data on the CRF titled “End of Observation” should be documented:

- Diagnose of HTN and cardiovascular diseases (changes in comparison with Baseline visit):
 - HTN target organ damage,
 - risk factors of cardiovascular diseases,
 - cardiovascular diseases.
- HNT treatment:
 - Date of the last Edarbi® intake or prolongation of Edarbi® treatment,
 - Reason(s) for discontinuation of Edarbi® treatment,
 - planned HTN treatment (if applicable) (INN, trade name, dosage regimen (single and total daily dose),
 - assessment of Edarbi® treatment by investigator (very satisfied, satisfied, neutral, unsatisfied, very unsatisfied),
 - assessment of HTN treatment by investigator (very satisfied, satisfied, neutral, unsatisfied, very unsatisfied).
- Reason(s) for discontinuation of observation

For patients who will discontinue observation in this study for any reason but continue treatment with Edarbi®, the investigator needs to report that therapy with Edarbi® will be continued on the appropriate CRF entitled “End of Observation”.

10.6. Treatments to be documented in the study

All medications should be administered according to approved local SmPCs.

10.6.1. Documentation of the study medication

Due to non-interventional design of the study, the decision about particular HTN treatment strategy to the patient is taken by attending physician. Treatment of interest is Edarbi®. The study medication is not provided by the sponsor.

Edarbi® treatments will be registered in the CRF. The following information about Edarbi® treatment will be collected:

- start date of Edarbi®,
- end date of Edarbi® treatment or prolongation of Edarbi® treatment,
- single and total dose, dose regimen,
- reason(s) for discontinuation of Edarbi® treatment (if applicable).

Edarbi® should be administered according to the official prescribing information (The Russian SmPC). The starting dosage will be 40 mg per day. In case of insufficient efficacy the dosage could be increased up to 80 mg per day.

10.6.2. HTN treatment

In case of combination HTN-treatment all co-medications for HTN treatment should be registered in Case Report Form. For every type of co-medication following data should be documented:

- INN, trade name,
- dosage regimen (dose taken),
- duration of treatment.

10.6.3. Prior HTN treatment

Medication taken before start of the study is called prior medication. In case the patient already underwent HTN treatment during 12 weeks prior to start of Edarbi® treatment, details of the therapy should be recorded in the CRF.

10.6.4. Concomitant medication

Concomitant medication is any drug given in addition to the HTN treatment. These drugs may be prescribed by a physician or obtained by the patient over the counter. Concomitant medication is not provided by the sponsor.

The information about concomitant medication can be received both on base of medical records and on questions to patients (according to routine practice). During the visits the information about changes in the concomitant therapy is recorded. At each study visit, patients will be asked whether they have taken any medication other than the study medication (used from signing of informed consent through the end of the study).

All drugs and drug combination for concomitant medication will be registered in CRF. For every type of drug there will be documented trade name, INN, dosage regimen (dose taken), duration of treatment, indications.

The area of interest is on antidiabetic and antidiabetic drugs.

10.6.5. Follow-up HTN treatment

If a patient withdraws from study due to change of Edarbi® treatment, the follow-up prescribed HTN treatment should be documented in the CRF.

10.6.6. Pregnancy

If any patient is found to be pregnant during the study she should be withdrawn. The pregnancy should be reported immediately, using an AE report form.

All pregnancies in patient on active study drug will be followed up to final outcome. The outcome, including any premature termination, must be reported to the Sponsor. An evaluation of child wellness after the birth must be reported to the Sponsor.

10.7. Laboratory, instrumental exams, physical examination and vital signs to be documented in the study

All examinations (physical examination and vital signs, laboratory tests and other exams) will be performed in accordance with common clinical routine practice, routine practice of a particular medical institution. All examinations are solely based on the physician's decision about strategy of diagnostics and treatment.

All examinations should be registered in the CRF only the protocol required lab tests will be recorded in the CRFs if they are done in routine practice. The documentation of laboratory and instrumental tests will strictly follow clinical practice. The reference ranges for each protocol required lab test performed according to routine practice will be collected as well.

